#### **14.3.1.3 Secondary variables of the retrospective cohort**

- \* Characteristics of retrospective patient population, patterns of care and effectiveness of different treatment options used under routine conditions for advanced CSCC prior to Cemiplimab launch
- \* Safety data on study participants
- \* Proportion of patients surviving at month 3, 6, 9, 12, 18, 24 and up to months 36 from initiation of systemic therapy
- \* PFS defined as time from first documented systemic therapy initiation until progression or treatment discontinuation due death or end of follow up
- \* Patient demographics and baseline characteristics (incl. age, performance status etc.) at study entry
- \* TNM stage (AJCC or UICC)
- \* Patterns of treatment for the retrospective cohort.

#### **14.3.2 Statistical analyses**

##### **14.3.2.1 Primary analysis**

The primary analysis is descriptive. TTNT will be estimated and visualized for each cohort separately by Kaplan-Meier estimators. Median TTNT will be presented with 95%-confidence intervals. Potential predictors of TTNT will be analyzed using Cox proportional hazards regression.

##### **14.3.2.2 Secondary analysis**

All secondary outcomes will be analyzed descriptively.

The rate of ORR and 95%-confidence interval will be given for each cohort. In addition and in an exploratory way, the pooled rate and its 95%-confidence interval will also be given. Potential predictors of response will be analyzed using logistic regression and/or Factorial Multiple Correspondences Analyses.

For time to event parameters, Kaplan-Meier curves will be presented and median time to event will be estimated with corresponding 95%-confidence intervals.

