STUDY DESIGN & DURATION	
This is a non-interventional multicenter study in Germany, Austria and Switzerland. The study includes two cohorts of adult patients with advCSCC who receive either treatment with Cemiplimab (prospective cohort) or other therapeutic approaches (retrospective cohort).
 
Enrollment will take place at approx. 70 study sites. The selection of participating sites will attempt to capture a representative sample of advCSCC treating clinic and office based physicians to get data from a real world setting outside of clinical trials.
 
In each cohort 200 patients will be enrolled from Germany, Austria and Switzerland. The duration of follow up will be up to 36 months for each patient in the prospective cohort.
 
Patients who meet the inclusion criteria and have signed the informed consent form (Sanofi-ICF) (only in the prospective cohort) will be included in the study.

STUDY POPULATION	
Inclusion Criteria
 
For the prospective cohort:
 
 
a. Planned treatment with Cemiplimab for advCSCC according to SmPC
 
b. Able to understand and complete study-related questionnaires
 
c. Signed ICF
 
 
For the retrospective cohort:
 
 
d. Patients <math>\geq</math> 18 years with first diagnosed advCSCC (locally advanced or metastatic CSCC) between Jan/2012 and Aug/2019
 
e. From these patients only anonymous data will be collected. Thus no Sanofi-ICF is needed This procedure allows including data from patients who are no longer alive (planned).
 
 
Exclusion Criteria
 
For the prospective cohort:
 
 
a. Missing ICF
 
b. advCSCC of unknown primary origin
 
c. Any condition that, in the opinion of the study physician, may interfere with patient's ability to participate in the study, such as severe cognitive impairment or other comorbidities that would, in the opinion of the study physician, predictably prevent the patient from adequately completing QoL assessments.
 

	
For the retrospective cohort:
 
 
d. Patients enrolled in clinical trials with Cemiplimab for advCSCC treatment
 
e. advCSCC of unknown primary origin
 
 
Sample Size: 400 patients (200 patients in each cohort)

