### Primary objectives

*Prospective and retrospective cohort:* Primary objective for this Cemiplimab NIS is to evaluate the clinical outcomes in treatment of advCSCC as a result of TTNT. Assessments of the response are clinical observations of physician's choice.

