### 7.3 EVALUATION CRITERIA

Study examinations will take place at months 3, 6, 9, 12, 18, 24 and 36.

Survey of concomitant medication and Cemiplimab treatment will take place at all study examinations.

Tumor Evaluation will be conducted according to guidelines and evaluation according to RECIST v.1.1 (Appendix 16.2). Computed tomography (CT) scan or magnetic resonance imaging (MRI) of chest, abdomen and pelvis and additional tumor bearing areas as well as digital photography of cutaneous lesions are preferred methods.

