##### **Response**

Best response will be captured as assessed by the study site and may include clinical assessment, radiographic imaging, or symptom resolution. DOR will be defined as time from the time of initial response until documented tumor progression or death.

Study data will be summarized descriptively with consideration for the following:

- Time to next of treatment (TTNT) or death, ORR, Disease Control Rate (DCR), DOR, Time to respond, PFS, OS,
- TTTF including lack of response and discontinuation due to AE
- Incidence and timing of pseudo progression, if applicable
- Response after pseudo progression, if applicable
- Time to response following occurrence of pseudo progression, if applicable
- IrAEs, SAEs

- DSD
- Pain Reduction

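### The exploratory ORR pooled over the cemiplimab and pre-cemiplimab cohorts estimates no treatment's response rate; separately, sections 7.3 and 11.2.1 disagree on what counts as a response, and the CRF does not record which basis was used

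*Protocol*

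**What the plan says.** **Pooling.** Section 14.3.2.2, repeated in the synopsis, first plans the cohort results: "The rate of ORR and 95%-confidence interval will be given for each cohort". It then says that, as an additional and exploratory result, "the pooled rate and its 95%-confidence interval will also be given". There are only two cohorts. The prospective one starts cemiplimab. The retrospective one is there to describe "effectiveness of different treatment options used under routine conditions for advanced CSCC prior to Cemiplimab launch", for patients first diagnosed from January 2012 to August 2019. Each is to hold 200 patients.

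**Response.** Three places bear on what a response is:

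- Section 7.3: "Tumor Evaluation will be conducted according to guidelines and evaluation according to RECIST v.1.1". It refers to an Appendix 16.2 and names CT, MRI and photography as preferred methods.
- Section 11.2.1, under a heading that covers both cohorts: "Best response will be captured as assessed by the study site and may include clinical assessment, radiographic imaging, or symptom resolution".
- Section 6, under the primary (TTNT) objective for both cohorts: "Assessments of the response are clinical observations of physician's choice".

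In the CRF table of section 9, best response to systemic therapy has no definition, and the restaging response item is a yes/no entry.

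**The concern.** These are two separate defects.

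First, a rate pooled over two treatment cohorts needs a target. Here the cohorts differ in treatment, calendar period and way of data capture, and the mixing proportion is a recruitment quota. No objective in the synopsis or section 6 asks for a response rate over all treatments together. A single percentage with a tighter interval than either cohort's own can easily be quoted as the response rate of the study.

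Second, a patient whose symptoms resolve without measured tumour shrinkage can be a responder under section 11.2.1 and not under section 7.3. If the database does not hold the basis of each response, no later analysis can separate the two kinds. That affects the ORR of each cohort, the planned models for predictors of response, and the prospective DCR and DOR.

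**Working it through.** The protocol gives no planning figure for ORR, so there is none to reproduce. The figures below are illustrations.

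**Inputs**

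- Cohort sizes: 200 and 200 (synopsis).
- Cemiplimab ORR: 47% in metastatic disease (section 5.1, which also gives 43.6% for locally advanced disease).
- Retrospective ORR: not stated. Section 5.1 quotes 44% partial response with earlier therapies, without a complete-response figure. Assumed range: 15% to 44%.

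**Pooled rate.** Pooled ORR = (n1·p1 + n2·p2)/(n1 + n2). At 200:200 this is the midpoint of the two rates. The intervals are Clopper-Pearson 95% with n = 400.

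| Retrospective ORR (assumed) | Responders | Pooled ORR | 95% CI | Contains 47%? | Contains the retrospective rate? |
|---|---|---|---|---|---|
| 15% | 94 + 30 | 31.0% | 26.5 to 35.8% | no | no |
| 20% | 94 + 40 | 33.5% | 28.9 to 38.4% | no | no |
| 30% | 94 + 60 | 38.5% | 33.7 to 43.5% | no | no |
| 44% | 94 + 88 | 45.5% | 40.5 to 50.5% | yes | yes |

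Where the interval stops excluding both rates: each cohort rate lies (47 − p2)/2 points from the pooled rate. Near a pooled 42% the half-width is 1.96·√(0.42·0.58/400) = 4.8 points. The interval excludes both when (47 − p2)/2 > 4.8, that is, when p2 is below about 37%.

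**Dependence on the quota.** Hold the cohort rates at 47% and an assumed 20%, and change only the numbers enrolled:

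- 200:200 gives (94 + 40)/400 = 33.5%
- 200:100 gives (94 + 20)/300 = 38.0%
- 100:200 gives (47 + 40)/300 = 29.0%

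The result moves by 9 points with no change in either treatment's response rate. At 47% and 44% the same three splits give 45.5%, 46.0% and 45.0%, so the movement is then small.

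**Symptom-only responses.** If a fraction q of patients without a measured response is recorded as responding on symptoms, the recorded ORR is p + q(1 − p). The document gives no value for q, so a range is assumed:

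- q = 5%: 0.47 + 0.05·0.53 = 49.6%
- q = 10%: 0.47 + 0.10·0.53 = 52.3%
- q = 20%: 0.47 + 0.20·0.53 = 57.6%

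For comparison, the 95% CI for 94/200 is 39.9 to 54.2%, a half-width of about 7 points.

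**The response rules side by side.** Section 7.3 sets criteria based on tumour measurement, in a section about the month 3 to 36 examinations, which only the prospective cohort has. Section 11.2.1 covers both cohorts and accepts symptom resolution on an equal footing with imaging. Section 14.3.2.2 does not say which rule makes an ORR responder. The appendix that section 7.3 cites is not in the contents list, which shows one appendix (the amendment history); section 16.2 of the body deals with laws and regulations. In section 9 some items are called evaluation or medical examination, but they have no definition and are listed at baseline, so nothing shows that they capture the basis of a later response.

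**The case against.** The strongest reply is that the pooled rate is explicitly exploratory and additional. The cohort ORRs come first, all secondary outcomes are descriptive, and nothing is decided on the pooled figure. That stands, and it limits the weight of the first point. A reader might infer that pooling replaces or corrupts the main ORR results; the text does not support that.

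A reader might also infer that the pooled interval necessarily misses both cohort rates. It does so only under an assumption: at the 44% partial response quoted in section 5.1 it contains both. The lack of a target does not depend on that assumption, but the size of the distortion does.

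On the response rules, it is tempting to read three mutually exclusive definitions. The statement in section 6 stands under the TTNT objective and mainly reflects the non-interventional setting, and section 9 says that procedures are not mandated. The real conflict is between section 7.3 and section 11.2.1. Nor do the conflicting rules explain why the pooled rate lacks meaning; it would mix treatments under any rule.

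It might further be inferred that DCR and DOR are distorted differently in the two cohorts. The synopsis and sections 6 and 14.3.1 list them for the prospective cohort only; just the general list in section 11.2.1 suggests otherwise.

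Finally, the responder derivation may be in an analysis plan not shown here. Such a plan could choose a rule, but it could not recover a basis of assessment that was never recorded.

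**Conclusion.** Both points hold, as moderate ones that should be corrected.

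1. The pooled ORR estimates no treatment or population quantity, because its weights are an enrolment quota. With 47% for cemiplimab and an assumed 15% to 44% retrospectively it lies between 31.0% and 45.5%. Its interval excludes both cohort rates if the retrospective rate is below about 37%. If the retrospective rate is near 44%, the practical harm is small.
2. Sections 7.3 and 11.2.1 are unreconciled and the CRF as described does not record the basis of response. Each cohort's ORR and the prospective DCR and DOR can mix measured with symptom-only responses. On the assumed 5% to 20% of patients without a measured response being counted on symptoms, a 47% ORR would be recorded as 49.6% to 57.6%. The document does not say how common this would be.

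**What to change.** - Delete the pooled ORR and its interval from section 14.3.2.2 and from the synopsis. Keep the two cohort ORRs with their intervals. Do not put a crude between-cohort difference in its place: it would be confounded by the same differences in treatment, period and data capture, and would be just as easy to misquote.
- Reconcile sections 7.3 and 11.2.1, and align section 6, so that one definition of an ORR responder applies. Correct or supply the appendix that section 7.3 cites.
- Add one CRF field for the basis of each response assessment (imaging, photographs, clinical judgement, symptoms). It records what was done and mandates no procedure.
- Report ORR for all site-assessed responses and, on a separate line, for responses based on imaging or photographs.

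The cost is one sentence deleted in two places, a few aligned sentences, one CRF item and one table row. The measured line may rest on a selected subset, because imaging will not have been done for everyone in routine care or in the charts. The number of patients assessed on each basis should therefore be shown beside it.

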#### **14.4 INTERIM ANALYSIS**

It is planned to perform yearly interim analyses in addition to a final report at the end of the study.

## **15 TASK AND RESPONSIBILITIES**

### **15.1 RESPONSIBILITIES OF STUDY COMMITTEES**

The non-interventional study consist of the study committee and scientific director. The research director and the study committee advises the sponsor on the planning and performance of the project as well as the preparation of the publication(s) after the results become available.

### **15.2 RESPONSIBILITIES OF THE STUDY SITE(S)**

The study site will perform the study in accordance with this protocol, applicable local regulations and international guidelines.

It is the physicians' responsibility to:

- Obtain any required local or institutional administrative or ethics approval prior to initiating data collection
- Complete the eCRF and record all data pertinent to the study. She/he will ensure that the information reported in the CRF is precise and accurate
- Make data available for quality audits and respond to data queries on a timely basis

### **15.3 RESPONSIBILITIES OF SANOFI**

Sanofi is responsible for taking all reasonable steps and providing adequate resources to ensure the proper conduct of the study. Sanofi and Regeneron are responsible for reviewing and approving this protocol.

## **16 ETHICAL AND REGULATORY STANDARDS**

### **16.1 ETHICAL PRINCIPLES**

Prior to launching data collection, depending upon local regulations, country specific regulatory authority and/or Independent EC review and approval will be obtained by Sponsor or Delegate, participating physician if applicable by local regulation

### **16.2 LAWS AND REGULATIONS**

This study will be conducted in accordance with the guidelines for Good Epidemiology Practice. Each participating study site should locally ensure all necessary regulatory submissions (e.g.: IRB/IEC) are performed in accordance with local regulations including local data protection regulations.

#### **Premature Termination of the study**

The sponsor has the right to terminate the study prematurely. Should the sponsor decide to terminate the study, the study site(s) will be notified in writing.

#### **Close-out of a site**

The sponsor and the study site have the right to close-out a site prematurely.

#### **Physicians Decision**

The physician must notify the sponsor of a desire to close-out a site in writing, providing at least 30 days' notice. The final decision should be made through mutual agreement with the sponsor. Both parties will arrange the close-out procedures after review and consultation.

#### **Sponsor's Decision**

The sponsor will notify the study site(s) of a decision to close-out a study site in writing. Reasons may include the following, among others:

- The study site has received all items and information necessary to perform the study, but has not enrolled any patient within a reasonable period of time
- The study site has violated any fundamental obligation in the study agreement, including but not limited to, breach of the applicable laws and regulations,
- The total number of patients required for the study is enrolled earlier than expected

In all cases, the appropriate IRB/EC and Health Authorities must be informed according to applicable regulatory requirements, and adequate consideration must be given to the protection of the patients' interests.

## **17 ADMINISTRATIVE EXPECTATIONS**

### **17.1 RECORD RETENTION IN STUDY SITES**

The study site must retain all essential study documents, including ICFs, source documents, copies of CRFs for at least 25 years following the completion or discontinuation of the study, or longer if a longer period is required by relevant regulatory authorities.

It is recommended that the study site retains any study documents after the completion or discontinuation of the study, unless otherwise specified in additional standards and/or local laws. However, applicable regulatory requirements should be taken into account in the event that a longer period is required.

### **17.2 CONFIDENTIALITY**

All material, information (oral or written) and unpublished documentation provided to the study site (or any action carried out by Sanofi and Regeneron on their behalf), including the present protocol and the eCRF, are exclusive property of Sanofi and Regeneron.

These materials or information (both global and partial) cannot be given or disclosed by the physician(s) or by any person of her/his group to unauthorized persons without the prior formal written consent of Sanofi and Regeneron.

The physician shall consider as confidential all the information received, acquired or deduced during the study and will take all necessary steps to ensure that there is no break of confidentiality, other than for information to be disclosed by law.

### **17.3 DATA PROTECTION**

The study site must take all appropriate measures to ensure that the anonymity of each study patient will be maintained. Patients should be identified by patient identification number, only, on eCRFs or other documents submitted to the sponsor. Documents that will not be submitted to the sponsor (e.g., signed ICF) must be kept in strict confidence.

The patient's and study site personal data, which may be included in the sponsor database, will be treated in compliance with all applicable laws and regulations. The sponsor shall take all appropriate measures to safeguard and prevent access to this data by any unauthorized third party.

No personally identifiable data will be included in Sanofi and Regeneron's database, nor its designee. All data shall be treated in compliance with all local applicable laws and regulations. When archiving or processing personal data pertaining to the study site

and/or to the patients, Sanofi and Regeneron and its designee shall take all appropriate measures to safeguard and prevent access to this data by any unauthorized third party.

#### **17.4 SANOFI AND REGENERON AUDITS BY REGULATORY AGENCIES**

Due to the nature of this study, audits are unlikely. However, in the event of any audit by a competent authority, the study site agrees to allow authorities to have direct access to his/her study records for review, being understood that these personnel are bound by professional secrecy, and as such will not disclose any personal identity or personal medical information.

The study site will make every effort to help with the performance of the audits giving access to all necessary facilities, data, and documents.

This study may be subject to a quality assurance audit by the sponsor or regulatory authorities. Should this occur, the physician is responsible for:

- Providing access to all necessary facilities, study data, and documents for the audit
- Taking all appropriate measures requested by the sponsor to resolve the problems found during the audit

Documents subject to audit include but are not limited to all source documents, CRFs, medical records, correspondence, ICFs, institutional review board (IRB)/ EC files, In addition, representatives of the sponsor may observe the conduct of any aspect of the clinical study or its supporting activities both within and outside of the study site(s) institution.

In all instances, the confidentiality of the data must be respected.

#### **17.5 PREMATURE DISCONTINUATION OF THE STUDY OR PREMATURE CLOSE-OUT OF A SITE**

Sanofi and Regeneron can decide at any time and for any reason to prematurely stop or to interrupt the study; the decision will be communicated by MDA in writing to the study site.

Similarly, should the study site decide to withdraw from the study, she/he will have to immediately inform MDA in writing.

If appropriate, according to local regulations, Ethic Committee(s) (IRB/IEC) and Competent Authorities should be informed.

## **17.6 OWNERSHIP AND USE OF DATA AND STUDY RESULTS**

No use of the data will be possible without the authorization of Sanofi and Regeneron. Sanofi and Regeneron will have full access to the final de-identified data allowing for appropriate academic analysis and reporting of the study results.

## **17.7 PUBLICATIONS**

Sanofi / Regeneron are responsible for presentations and/or publications. The study results must be submitted for review by Sanofi/Regeneron before publication.

All study sites give full authority to the Sanofi/Regeneron for primary presentation and/or primary publication of results. No other publication is allowed before the primary publication. Any subsequent presentation or publication by a study participant (including for substudies) must be approved by Sanofi/Regeneron and make reference to the study and the primary publication.

The final decision to publish any manuscript/ abstract/ presentation will be made by Sanofi and Regeneron allowing for internal review and comments.

All manuscript/ abstract/ presentation must be submitted to the internal review of Sanofi and Regeneron at least forty-five (45) calendar days in advance of submission, unless a previously agreed upon timeline is available. Sanofi and Regeneron may request that its name and/or names of one or several of its employees appear or do not appear in such publication, except where study funding disclosures are required by journal policy.

Sanofi and Regeneron can delay publication or communication for a limited time in order to protect the confidentiality or proprietary nature of any information contained therein.

## **AUTHORSHIP CRITERIA**

Physicians from each country may be considered for authorship on manuscripts ensuing from this study. Authorship will be considered based upon physicians

1) meeting International Committee of Medical Journal Editors (ICMJE) guidelines, and  
2) based upon volume of patient enrollment within each country. ICMJE guidelines require:

1. Substantial contributions to the conception or design of the work; or the acquisition, analysis, or interpretation of data for the work; AND
2. Drafting the work or revising it critically for important intellectual content; AND
3. Final approval of the version to be published; AND
4. Agreement to be accountable for all aspects of the work in ensuring that questions related to the accuracy or integrity of any part of the work are appropriately investigated and resolved.

